#### **8.3.2.10. Lewy Body Composite Risk Score (LBCRS)**

The LBCRS is a scale that has been shown to help discriminate DLB from other causes of dementia, such as Alzheimer's disease, using a cut-off score of 3 (Galvin, 2015). LBCRS will be administered during screening to collect baseline information regarding the clinical presentation of DLB symptoms.

#### **8.3.2.11. CT scan or MRI**

An MRI or CT scan will be performed between Visit 1 and Visit 2 if no scan has been performed within the 12 months prior to the Screening Visit. These scan findings must be consistent with the diagnosis of dementia due to DLB without any other clinically significant pathologies.

#### **8.3.2.12. PET or SPECT**

A PET or SPECT scan PET / SPECT imaging is not required. However, it may be performed during Screening for eligibility per inclusion criterion number 1.

### **8.3.3. Pharmacokinetics**

Blood samples for PK analysis of RVT-101 will be collected during the study visits indicated in [Section 8.1](#). The actual date and time of each blood sample collection will be recorded, as well as the date and time of the previous dose of IP. The timing of PK samples may be altered and/or PK samples may be obtained at additional time points to ensure thorough PK monitoring.

Two PK samples per subject will be taken for the purpose of assessing plasma concentrations of RVT-101 at the following specific time points:

- At Visit 6 (Week 4), the blood sample should be taken after cognitive testing, ECG, questionnaire for dizziness and falls, and vital signs measurements have been performed.
- At Visit 8 (Week 8), the blood sample should be taken after cognitive testing, ECG, questionnaire for dizziness and falls, and vital signs measurements have been performed.
- Unscheduled PK samples may be requested by Axovant Sciences or the Medical Monitor after discussion with investigators (e.g., in cases of suspected drug toxicity).

The samples will be centrifuged and the resulting plasma will be shipped to a central laboratory. Further details with regard to shipping, collection, and processing of samples are provided in the laboratory manual.

Plasma analysis will be performed under the control of Axovant Sciences. Concentrations of RVT-101 and RVT-101 metabolites will be determined in plasma samples using the currently approved bioanalytical methodology. Raw data will be archived at the bioanalytical site.

Once the plasma has been analyzed for RVT-101, any remaining plasma may be analyzed for other compound-related metabolites and the results reported under a separate protocol.

## **9. DATA MANAGEMENT**

For this study subject data will be entered into Axovant Sciences defined eCRFs, transmitted electronically to Axovant Sciences or designee, and combined with data provided from other sources in a validated data system.

Management of clinical data will be performed in accordance with applicable Axovant Sciences' or its representative's standards and data cleaning procedures to ensure the integrity of the data, e.g., correcting errors and inconsistencies in the data.

AEs and medical history terms will be coded using an agreed version of the Medical Dictionary for Regulatory Activities (MedDRA), using Axovant Sciences' or its representative's coding conventions.

Concomitant medications will be coded using the WHO ATC classification ([http://www.whocc.no/filearchive/publications/1\\_2013guidelines.pdf](http://www.whocc.no/filearchive/publications/1_2013guidelines.pdf)).

The eCRFs (including queries and audit trails) will be retained by Axovant Sciences, and copies will be sent to the investigator to maintain as the investigator copy.

## 10. STATISTICAL CONSIDERATIONS AND DATA ANALYSES

### 10.1. Hypotheses

The primary statistical framework will be to demonstrate superiority of RVT-101 over placebo.

The null hypothesis is as follows, with a significance level of  $\leq 0.05$  needed for the null hypothesis to be rejected.

- There is **NO** statistically significant difference between Intepirdine and placebo in the mean change from baseline to Week 24 in the UPDRS- III.
- There **IS** a statistically significant difference between Intepirdine and placebo in in the mean change from baseline to Week 24 in the UPDRS- III.

The individual Intepirdine arms will be tested, as follows:

- Intepirdine 70 mg vs placebo
- Intepirdine 35 mg vs placebo

All hypothesis tests will be 2-sided, performed at the 5% level of significance.

The primary endpoint needs to achieve a significance level of 0.05 within an Intepirdine dose to allow for testing of the secondary endpoints within that dose.

### 10.2. Sample Size Considerations

The sample size is based on assumptions of treatment benefit for one primary endpoint, the UPDRS- III total score. A sample size of 70 subjects per treatment group will allow a treatment difference of 4 points between placebo and active treatment in the change from baseline in UPDRS- III score to be detected with 88% power and a 0.05 significance level assuming an underlying standard deviation (SD) of 7.5

There are two secondary endpoints:

- ADAS-Cog 11 total score. A sample size of 80 subjects per treatment group will allow a treatment difference of 3 points between placebo and active treatment in the change from baseline in ADAS-Cog-11 score to be detected with 88% power and a 0.05 significance level assuming an underlying standard deviation (SD) of 6. Under the assumptions of a 2.5, 2.0 and 1.5-point treatment effect, the power is 74%, 55% and 35%, respectively.
- CIBIC+. A sample size of 80 subjects per treatment group will allow a treatment difference of 0.5 points between placebo and active treatment in the observed values in the CIBIC+ to be detected with 91% power and a 0.05 significance level assuming an underlying standard deviation (SD) of 0.95. Under the assumptions of a 0.4 and 0.3-point treatment effect, the power is 75% and 51%, respectively. Randomization will be stratified according to Baseline MMSE score in the groupings of 14-17 points, 18-21 points and 22-26 points and according to whether subjects are or are not taking a cholinesterase inhibitor as a concomitant medication.

Randomization will be stratified according to Baseline MMSE score in the groupings of 14-17 points, 18-21 points and 22-26 points and according to whether subjects are or are not taking a cholinesterase inhibitor as a concomitant medication.

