## **5. STUDY DESIGN**

### **5.1. Overall Design**

This is a multi-center, double-blind, randomized, placebo-controlled, parallel-group study in patients with probable DLB who are either not receiving therapy for DLB or are receiving a stable regimen of standard therapy for DLB. The efficacy and safety of RVT-101 at doses of 70 mg and 35 mg daily will be evaluated over a 24-week treatment period. All subjects who are on stable doses of other therapies to treat cognitive deficits and/or hallucinations associated with DLB will continue to remain on them for the duration of the study. Approximately 240 subjects will be randomized. The randomization ratio will be 1:1:1 (70 mg RVT-101: 35 mg RVT-101: placebo). The primary endpoint will be measured after 24 weeks of treatment. Study participation will last approximately 32 weeks: 0 to 4 weeks for Screening, a 2-week Single-Blind Run-In Period to evaluate baseline status, a 24-week randomized, double-blind, placebo-controlled Treatment Period and a 2-week Safety Follow-up Period for subjects who do not enter the extension study RVT-101-2002.

There will be weekly clinical assessments for the first two weeks of double-blind treatment, bi-weekly assessments thereafter until 12 weeks post-randomization and every six weeks thereafter. For certain visits (Visits 5, 7 and 9), subjects may have the option of whether to have assessments performed at the clinical study site or by a trained, visiting nurse in their own home.

[figure not shown]
An independent Safety Monitoring Committee (SMC) will review interim safety data accumulated after approximately 30 subjects have completed 4 weeks of double-blind treatment and throughout the study at points specified in the SMC Charter. The SMC will provide their recommendation regarding the acceptability of reducing the visit frequency by omitting certain visits (Visits 5, 7 and 9) for both newly enrolled subjects and subjects active in the study at the time of the recommendation. Study enrollment will not be stopped or slowed to wait for SMC's recommendation and will proceed as planned with all visits until the SMC recommendation is made. Site will be formally notified of the SMC's recommendation regarding whether or not Visits 5, 7 and 9 can be omitted.

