#### **6.6. Withdrawal Criteria**

##### **6.6.1. Reasons for Withdrawal**

A withdrawal from the study is defined as withdrawing any time after entering the Single-Blind Run-In Phase and before completion of the Week 24 Visit (Visit 12). Subjects who permanently discontinue use of investigational product (IP) will be considered to be withdrawn from the study and will not be allowed to rescreen. Subjects may withdraw from the study at any time and for any reason. The investigator (or designee) must document the reason for withdrawal in the electronic case report form (eCRF). Information related to AEs will continue to be collected as per usual procedures on subjects who have discontinued IP. Withdrawn subjects will not be replaced. The reasons for subject withdrawal will be recorded and may include, but are not limited to:

- Any clinical AE, laboratory abnormality, or other medical condition or situation occurs such that continued participation in the study would not be in the best interest of the subject in the opinion of the investigator.
- Pregnancy of female subject (discontinuation of treatment, but will be followed until the outcome of pregnancy is known)
- Significant protocol violation
- Subject requests to discontinue for any reason; it is important to determine whether the withdrawal of consent is primarily due to an AE, lack of efficacy, or other reason.
- Sponsor decision to withdraw the subject or terminate the study, if it is considered in the best interest of the subject or study.

The above reasons do not automatically lead to withdrawal from the study in all cases. The final decision will be based on consultation between the principal investigator and the study Medical Monitor, with the ultimate decision by the principal investigator, subject or caregiver, except in cases where the Sponsor decides to terminate the study or withdraw the subject from the study.

If a subject meets discontinuation criteria during treatment, an Early Termination Visit will be required ([Section 6.6.2](#)).

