## 6. SAMPLE SIZE CONSIDERATIONS

The sample size is based on assumptions of treatment benefit for one primary endpoint, the UPDRS- III total score. A sample size of 70 subjects per treatment group will allow a treatment difference of 4 points between placebo and active treatment in the change from baseline in UPDRS- III score to be detected with 88% power and a 0.05 significance level assuming an underlying standard deviation (SD) of 7.5

There are two secondary endpoints:

- ADAS-Cog 11 total score. A sample size of 80 subjects per treatment group will allow a treatment difference of 3 points between placebo and active treatment in the change from baseline in ADAS-Cog-11 score to be detected with 88% power and a 0.05 significance level assuming an underlying standard deviation (SD) of 6. Under the assumptions of a 2.5, 2.0 and 1.5 point treatment effect, the power is 74%, 55% and 35%, respectively.
- CIBIC+. A sample size of 80 subjects per treatment group will allow a treatment difference of 0.5 points between placebo and active treatment in the observed values in the CIBIC+ to be detected with 91% power and a 0.05 significance level assuming an underlying standard deviation (SD) of 0.95. Under the assumptions of a 0.4 and 0.3 point treatment effect, the power is 75% and 51%, respectively.

Randomization will be stratified according to Baseline MMSE score in the groupings of 14-17 points, 18-21 points and 22-26 points and according to whether subjects are or are not taking a cholinesterase inhibitor as a concomitant medication.

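### ADAS-Cog 11 and CIBIC+ power is stated on all 80 randomised subjects per arm, so it holds only with essentially no loss to Week 24; the primary's 70 per arm is unexplained

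*Protocol*

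**What the plan says.** Protocol 5.1: "Approximately 240 subjects will be randomized", in a 1:1:1 ratio, which is 80 per arm.

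The power statements are the same in Protocol 2, Protocol 10.2 and SAP 6:

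- UPDRS-III (primary): "A sample size of 70 subjects per treatment group will allow a treatment difference of 4 points", SD 7.5, 88% power.
- ADAS-Cog 11 (secondary): "A sample size of 80 subjects per treatment group will allow a treatment difference of 3 points", SD 6, 88% power; 74%, 55% and 35% for 2.5, 2.0 and 1.5 points.
- CIBIC+ (secondary): "A sample size of 80 subjects per treatment group will allow a treatment difference of 0.5 points", SD 0.95, 91% power; 75% and 51% for 0.4 and 0.3 points.

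Protocol 6.6.1 treats permanent discontinuation of study drug as withdrawal from the study and adds: "Withdrawn subjects will not be replaced". Protocol 10.4.2 and SAP 9.4.1 analyse both secondary endpoints with an MMRM like that of the primary, which uses observed values without imputation. Neither document gives a dropout rate, says whether 70 or 80 is a randomised or an evaluable number, or explains why they differ.

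**The concern.** One section uses two sample sizes for endpoints read at the same Week 24 visit. The primary is powered on 70 per arm. The secondaries are powered on 80, which leaves no room for loss over 24 weeks of treatment in people with dementia.

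The plan itself expects loss. It defines a Completers population separate from ITT, tabulates missing-data patterns for the primary endpoint, and schedules LOCF and multiple imputation as sensitivity analyses for the secondaries.

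What is at stake is interpretation. If a dose succeeds on UPDRS-III and then misses on ADAS-Cog 11 or CIBIC+, readers will set the miss against 88% or 91% power. The design has that power only with complete data.

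**Working it through.** **Inputs.** Two-sided 5% tests, pairwise against placebo (Protocol 10.1). Differences, SDs and numbers per arm are those of Protocol 10.2.

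**Formula.** Two-sample t-test with n per arm: noncentrality = Δ / (SD × √(2/n)), with 2n − 2 degrees of freedom. Power is the noncentral-t probability beyond the two critical values.

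**Step 1: reproduce the headline figures at their own n.**

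- UPDRS-III, n = 70: 4 / (7.5 × √(2/70)) = 3.155; critical t on 138 df = 1.977; power 88.0% (stated 88%).
- ADAS-Cog 11, n = 80: 3 / (6 × √(2/80)) = 3.162; critical t on 158 df = 1.975; power 88.2% (stated 88%).
- CIBIC+, n = 80: 0.5 / (0.95 × √(2/80)) = 3.329; same critical value; power 91.1% (stated 91%).

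On 80 per arm, the secondaries' basis, UPDRS-III power would be 91.8%. So the plan did use two different bases.

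**Step 2: all secondary figures at 80 and, for comparison, at 70.**

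| Endpoint, difference | Stated | n = 80 | n = 70 |
|---|---|---|---|
| ADAS-Cog 11, 3.0 | 88% | 88.2% | 83.6% |
| ADAS-Cog 11, 2.5 | 74% | 74.5% | 68.7% |
| ADAS-Cog 11, 2.0 | 55% | 55.4% | 49.9% |
| ADAS-Cog 11, 1.5 | 35% | 34.9% | 31.2% |
| CIBIC+, 0.5 | 91% | 91.1% | 87.1% |
| CIBIC+, 0.4 | 75% | 75.4% | 69.6% |
| CIBIC+, 0.3 | 51% | 51.0% | 45.8% |

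All seven figures reproduce at 80. At 70 each is about 4 to 5 points below the stated value.

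**Step 3: range over assumed loss.** The documents give no rate, so these losses are assumptions. Evaluable n = 80 × (1 − loss).

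| Assumed loss | n per arm | ADAS-Cog 11, 3 points | CIBIC+, 0.5 points |
|---|---|---|---|
| 0% | 80 | 88.2% | 91.1% |
| 5% | 76 | 86.5% | 89.7% |
| 10% | 72 | 84.6% | 88.0% |
| 12.5% | 70 | 83.6% | 87.1% |
| 20% | 64 | 80.1% | 84.0% |

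The table treats a lost subject as contributing nothing. The MMRM can recover part of that, so for a given dropout rate these are cautious values.

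**The case against.** **No arithmetic error.** Each power statement is conditional on its stated number and is true on that condition. A reader might infer that the figures were miscalculated. Step 1 and Step 2 show they were not. This stands.

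**The 70 may belong to UPDRS-III alone.** A reader might infer that 70 is the evaluable number for every endpoint and that 83.6% and 87.1% are the correct powers. It is true that 80 × (1 − 0.125) = 70, but neither document calls 70 a dropout-adjusted number. UPDRS-III is analysed in a narrower population (Protocol 10.3.1, SAP 7.4), which removes certain ITT subjects whose anti-parkinsonian medication was increased. The secondaries use the full ITT population, so a smaller number for the primary is to be expected. This stands, although the plan does not give it as the reason, and it cannot make all 80 evaluable.

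**MMRM keeps partial data.** Subjects who leave early still contribute ADAS-Cog at Week 12 and CIBIC+ at Weeks 4, 8, 12 and 18. This stands in part, and more for CIBIC+. A subject who leaves before Week 12 would, as Table 2 of the protocol reads, have no post-baseline ADAS-Cog. That subject can still be in ITT, because a post-baseline UPDRS-III is enough. The ITT count can therefore exceed the number with usable ADAS-Cog data.

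**Covariates may offset the loss.** If the SD of 6 is unadjusted, covariates explaining 12.5% of the variance would cancel a fall from 80 to 70, since (1 − 0.125)/70 = 1/80. The documents do not say whether the SD is adjusted. The argument is weaker for CIBIC+, whose model has no baseline value.

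**Little depends on it.** The sample size rests on the primary endpoint alone, and the secondaries are tested within a dose only after the primary succeeds there. This stands, and it limits the weight of the point.

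**Conclusion.** The point holds as an unexplained zero-loss basis for the secondary powers. The stated 88/74/55/35% and 91/75/51% are right for 80 evaluable subjects per arm. But 80 is the whole randomised number, withdrawals are not replaced, and the primary in the same section is powered on 70 without explanation. Under the plan's own assumptions, the secondary powers hold only with essentially no loss to Week 24.

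The size depends on a loss rate the documents do not give. At about 6% loss (n = 75) the headline powers are 86.0% and 89.3%, within 2 points of those stated. At 10% to 20% they run from 84.6% down to 80.1% for ADAS-Cog 11 and from 88.0% down to 84.0% for CIBIC+. These values assume the plan's SDs, an unadjusted t-test and no information from lost subjects.

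A reader might also infer that the trial is too small. The documents do not support that: the trial is sized on UPDRS-III, and its 88% power at 70 per arm reproduces.

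**What to change.** In Protocol 2, Protocol 10.2 and SAP 6:

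1. Say whether 70 and 80 are randomised or evaluable numbers, and why they differ. If the UPDRS-III exclusion is part of the reason, say so.
2. Give the loss assumed for each endpoint and its source.
3. Restate the ADAS-Cog 11 and CIBIC+ powers, including those for the smaller differences, on the number of ITT subjects expected to have usable data for that endpoint. If that number is 70, the headline figures become about 84% and 87%. If the sponsor relies on partial data or covariate adjustment to justify a larger effective number, state that assumption.

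This is a change of text in three places. The secondary powers will read slightly less favourably. No subjects are added, and the tests, the significance level and the primary's 88% power stay as they are.

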### **10.3. Data Analysis Considerations**

#### **10.3.1. Analysis Populations**

It is intended that a complete accounting of patients for the analysis populations will be provided, from the Screening Population through the Per-Protocol Population.

- Screening Population: All patients who are screened (signed an informed consent) will be included in the Screening Population.
- Placebo Run-In Population: All patients who took at least 1 dose of IP in the Placebo Run-in will be included in the Placebo Run-In Population. This population will be used to provide an accounting of the disposition of patients during this phase of the study.
- Randomized Population: The Randomized Population will include all patients who are randomized.
- Safety Population: All subjects who were randomized and took at least one dose of double-blind investigational product.
- Intent-to-Treat (ITT): All subjects randomized to treatment who have taken at least one dose of double-blind IP and who have a baseline and at least one post-baseline efficacy assessment for the UPDRS-III *or* for the ADAS-Cog 11. This will be the primary population used for the efficacy analysis of all variables EXCEPT the UPDRS Part III and Part 5. In analyses using this population, subjects will be grouped according to their randomized treatments.
- UPDRS Primary Analysis Population: This will be the primary population used for the UPDRS Part III efficacy analysis, and is comprised of all ITT patients EXCLUDING those with no change OR a worsening in UPDRS-III total score prior to a dose increase in anti-parkinsonian medications and where there is *subsequent* improvement or stabilization of UPDRS-III total score.
  - Dose increase in anti-parkinsonian medication is defined as an increase in dose, dose frequency or commencement of the medication where the total daily dose of the medication at Week 24 is higher than at Baseline.
- UPDRS Sensitivity Analysis Population: All ITT patients EXCLUDING those who increase or start an anti-parkinsonian medication during the double-blind treatment period.
  - Dose increase in an anti-parkinsonian medication is defined as an increase in dose or frequency or commencement of the medication where the total daily dose of the medication at Week 24 is higher than at Baseline.
- Completers (CS) Population: ITT subjects who have completed the Week 24 visit with non-missing endpoints for all three variables, the UPDRS-III, ADAS-Cog 11,

and CIBIC+. This population will be used for supportive analysis of the primary efficacy variable and other cognition and efficacy endpoints.

- Pharmacokinetics (PK) Population: All subjects in the Safety Population who undergo plasma PK sampling and have at least one post-baseline evaluable PK concentration result.
- Per-Protocol (PP) Population: Subjects in the ITT Population who have no major protocol violations. The PP Population will not be analyzed if this population comprises more than 95% or less than 50% of the ITT Population. This population will be used for confirmatory analysis of the primary efficacy variable and the two secondary efficacy variables. The PP Population will be identified prior to breaking the study blind.

### **10.3.2. Interim Analysis**

No interim analyses are planned.

## **10.4. Key Elements of Analysis Plan**

All hypothesis tests and confidence intervals will be two-sided at an alpha level of 5%. For statistical analysis and use in models, sites will be pooled by geographical region or size. The method of grouping sites will be defined prior to unblinding the study and described in the Statistical Analysis Plan (SAP).

All efficacy and safety measures over the course of the study will be presented. Continuous data will be summarized by means, SDs, medians, maximum, minimum, and numbers of subjects. Categorical data will be summarized by counts and percentages. Data will be tabulated by treatment group.

### **10.4.1. Primary Efficacy Analyses**

The primary efficacy endpoint is the change from Baseline in the UPDRS-III total score at Week 24. The primary method of analysis will be using a mixed model for repeated measures (MMRM), with supportive method being the Wilcoxon rank statistic (a nonparametric test).

For the primary efficacy and secondary efficacy variable ONLY, in addition to the primary pairwise analyses, a table will be presented that will compare the POOLED data (pooled across the 35 mg and 70 mg Intepirdine arms) vs placebo. This will be done ONLY for the MMRM analysis.

Primary treatment comparisons between Intepirdine and placebo will be performed on the change from Baseline to Week 24 using an MMRM with restricted maximum likelihood estimation, an unstructured covariance matrix, and the Kenward-Roger approximation for denominator degrees of freedom. The model will include terms for treatment, visit, treatment by visit interaction, pooled geographic region, baseline MMSE score, the baseline value, and the baseline value by visit interaction.

As additional supportive information, treatment differences at each post baseline visit will also be derived using the MMRM model; however, primary inferences will be drawn from treatment differences derived from the MMRM models at Week 24.

The estimated treatment difference (“Intepirdine 35mg – Placebo” and “Intepirdine 70mg – Placebo”) at each visit will be displayed in the summary of statistical analysis together with the 95% confidence interval and the associated p-value.

No imputation of the missing values will be performed for the primary analyses, ie, the data used in the analysis will be the actual observed responses at each visit.

Least Squares Means for each visit will also be presented with the standard error and the number of subjects contributing to the Least Squares Means. Least Squares Means and estimated treatment differences for each visit and the associated 95% confidence interval will be displayed graphically.

The nature of missing data will be explored and the extent of missing data pattern will be summarized. Details will be provided in the SAP.

